## 7.4 Purpose of Safety Analyses

The safety run-in phase will be conducted in the first 3 treated patients for at least 6 weeks after TG4050 first dose. Each patient will be monitored for 4 weeks after the first injection of TG4050 before the next patient can be enrolled.

During the safety run-in phase, the study may be suspended and an IDMC ad-hoc meeting immediately called if at least one of the following events occurs:

- any grade  $\geq 3$  toxicity that is at least possibly related to TG4050, with the following exception: pre-existing grade 2 fatigue at baseline that would worsen up to grade 3
- any death.

Beyond the safety run-in phase, the study may be suspended or terminated under any of the following circumstances:

- Sponsor's decision
- Health's Authorities' decision
- Any death, unrelated to progressive disease, which occurs within 30 days after TG4050 administration
- IDMC recommendation in case of a safety concern. However, in this case, the final decision as to whether or not continue the study will be taken by Transgene.

If the study needs to be terminated, Transgene and the Investigator will assure that adequate consideration is given to the protection of the patients. Transgene will notify the Health Authorities and the IEC(s)/IRB(s), any other committees of the premature study termination according to local regulations.

## 7.5 Final Statistical Analysis

Drafts TFLs will be produced and reviewed before the database export to ensure that no critical data is missing and to check potential inconsistency in the database.

Final Analysis will be performed when all patients completed study treatment up to 20 injections or withdrew for any reasons.

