#### **6.2.4. End of treatment visit**

An end of treatment visit will be performed within 7 days after study treatment is completed or stopped for whatever reason (disease progression, unacceptable toxicity including dose-limiting toxicity or, patient withdrawal due to any reason). The end of treatment visit and the last visit planned for treatment administration can be performed on the same day provided that all evaluations and blood samples required at both visits are performed (except if repeated exams).

The following evaluations will be conducted:

- Physical examination, including vital signs and weight
- PS on ECOG scale
- Adverse events reporting
- Concomitant medications
- CBC including RBC, Hb, WBC and differential, platelets
- Biochemistry tests
- Electrocardiogram
- Reporting of subsequent cancer therapy if applicable
- For translational research, a blood sample and tumor sample will be collected at the time of documented disease progression when clinically feasible.
- Cytapheresis: in case patient is withdrawn prior to Day 64, a cytapheresis is to be performed at the end of treatment visit. If not clinically feasible, it can be replaced by a 150 ml blood draw.

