#### **6.2.6. Safety Follow-up visit**

A safety follow-up visit will be performed at least 30 days (+14 days allowed) after the last dose of study treatment.

The following evaluations will be conducted and recorded in eCRF:

- Physical examination, including vital signs and weight
- PS on ECOG scale
- Adverse events reporting
- Concomitant medications
- Reporting of subsequent cancer therapy if applicable

For patients who refuse to return for a visit, they will be contacted by phone to obtain this information if possible.

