**8.2.2.2. Time period for collection**

From the date of signature of ICF and up to first TG4050 administration, only serious adverse reactions (SARs) caused by a protocol-required procedure will be collected and reported (refer to section 8.2.2. and 8.2.3). The only protocol-required procedure concerned is the specific blood sample taken during the screening period.

AEs, SAEs, or procedure related ARs that occur between ICF signature and 3 weeks prior to first administration, and that are considered by the investigator as particularly relevant to the patient's condition, will be collected as a current medical history.

If an event occurs during the period from 21 days before and up to first TG4050 administration, it will be recorded either on a "Medical history/current conditions" page for an identified syndrome (e.g., pneumonia) or on a "Signs and symptoms" page for symptoms with no associated syndrome (e.g., diarrhea).

From the first TG4050 administration and in case of worsening of a sign and symptoms which started 21 days before first TG4050 administration, an AE page will be completed using a verbatim starting by "worsening of..."

From the initiation of TG4050 treatment up to the safety follow-up visit (at least 30 days after the last administration of study treatment), all AEs and SAEs should be collected and recorded on the eCRF. During this period all SAEs should also be reported to Transgene.

All SARs related to a study specific procedure occurring during the screening period and all SAEs occurring during the treatment period will be recorded in Transgene safety database.

SAEs occurring more than 30 days after administration of the last dose of TG4050 and evaluated by the investigator as related to TG4050 should be collected and reported to Transgene indefinitely even after study closure. These will however not be reported in the eCRF after Database lock.

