## 7.6 Definitions and Derived variables

### 7.6.1 Definitions

Screened patient: A patient having consented

Re-screened patient: A patient who did not meet eligibility criteria when initially consented. This patient may fulfill criteria later and will be re-consented for screening.

Screened failed patient: A screened patient never treated in the study for any reason.

Treated patient: A patient having received at least one TG4050 dose.

Completed patient: Patient will be considered as completer if she received the treatment until:

- Disease progression or until the maximum number of administrations has been reached (20 injections of TG4050)
- occurrence of an AE due to DLT or linked to progressive disease
- Death

Baseline: Unless otherwise specified, baseline is the last measurement taken prior to the first injection of TG4050.

Baseline assessment for efficacy evaluations: In the context of baseline definition, the efficacy evaluations include in particular tumor evaluations and CA125 measurement. If baseline assessment is missing, results obtained at Day 1 can be used if assessments were performed prior to first TG4050 injection.

Baseline assessment for safety evaluations: the last available assessment before first TG4050 injection. If patients have no assessment as defined above, the baseline result will be missing. Baseline can be D1 if assessment was done before first TG4050 injection.

Study day:

- From first treatment administration, study day will be calculated using the start date of treatment as the origin, i.e. the study day will be calculated as (date of assessment) – (start date of study treatment) +1. Then study day 1 will be the first day of first study treatment administration.
- For pre-study treatment administration measurements, the study day will be negative and calculated as (date of assessment) – (start date of study treatment).

Cut-off date: For a given analysis (safety, final and follow-up analysis), data in the database with a date prior or equal to the cut-off date must be as clean as possible for the analyses. The cut-off date will be the date of the export.

Time window (to check visits out of this window):

- For the visits:
  - +/- 1 day for the first 6 weeks
  - +/- 7 days beyond the first 6 weeks
- For the tumor assessment:

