##### **Treatment-emergent adverse Event (AE):**

A treatment-emergent adverse event (TEAE) is defined as a sign or symptom that emerges during treatment or within 30 days of the last dose of the study drug, having been absent pre-treatment or that has worsened relative to the pre-treatment state. Any adverse event deemed related to study drug will also be considered a TEAE regardless of elapsed time since last study drug dose.

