### 8.10.1.2 AEs analysis

#### Adverse Events

AE summaries will include all TEAEs corresponding to AEs that have started on or after the day of first study treatment administration or that have worsened on or after first TG4050 administration and starting no later than 30 days after the date of last study treatment administration.

For these analyses, the number and percentage of patients with at least one AE will be summarized in a frequency table by System Organ Class (SOC) and Preferred Term (PT) as per MedDRA dictionary. The number of events will also be summarized in the same table. Tables will be presented by SOC sorted in alphabetic order and PTs within SOC sorted by descending number of counts according to the overall column.

Written narratives will be produced for all SAEs and unexpected or other significant AEs that are judged to be of special interest because of their clinical importance.

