### 8.10.2 Laboratory abnormalities

The summaries will include all laboratory assessments collected from baseline assessment until 30 days after treatment discontinuation. All laboratory assessments will be listed and those collected more than 30 days after study treatment discontinuation will be flagged in the listings.

All laboratory values will be converted into SI units and will have a severity grade calculated using appropriate common terminology criteria for AEs (NCI-CTCAE, version 5). A listing of laboratory values will be provided by laboratory parameter and patient. A separate listing will display notable laboratory abnormalities (i.e., newly occurring CTCAE Grade 3 or 4 laboratory toxicities). The frequency of these notable laboratory abnormalities will be displayed by parameter. The shift tables using CTCAE grades to compare baseline to the worst post-baseline value will be produced for all relevant safety measures as described in the statistical analysis plan. Note that for parameters with two directions abnormalities (hypo/hyper), two tables will be presented.

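### SAP 7.5 lets the final analysis start when dosing ends, although the primary safety summaries run to 30 days after the last dose

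*SAP*

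**What the plan says.** **Timing rule.** SAP 7.5: "Final Analysis will be performed when all patients completed study treatment up to 20 injections or withdrew for any reasons". On the cut-off, SAP 7.6.1 says: "The cut-off date will be the date of the export". Neither passage asks for a minimum time since the last dose.

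**Window of the primary endpoint.** Protocol 9.3.1 makes adverse events the primary endpoint. SAP 8.10.1.1 treats an event as treatment-emergent if it "emerges during treatment or within 30 days of the last dose of the study drug", and adds drug-related events at any later time. The summaries in SAP 8.10.1.2 take in events "starting no later than 30 days after the date of last study treatment administration".

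**Collection.** Protocol 8.2.2.2 has all AEs and SAEs recorded from the first injection up to the safety follow-up visit. Protocol 6.2.6 fixes that visit: "A safety follow-up visit will be performed at least 30 days (+14 days allowed) after the last dose of study treatment". It is separate from the end-of-treatment visit, which Protocol 6.2.4 places within 7 days of stopping.

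**End of study.** SAP 7.6.1 defines the end of study as the last visit of the last patient and expressly includes the safety follow-up visit. SAP 7.5 does not refer to this definition.

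**The concern.** The rule for starting the analysis and the window of the endpoint being analysed do not fit together. A patient who receives injection 20 satisfies SAP 7.5 that same day, with none of the 30 post-dose days observed. If the database were exported then, the summaries would describe a 30-day window that had not elapsed for that patient.

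More than the overall AE count depends on this window. Beyond the run-in, a dose-limiting toxicity is a related treatment-emergent event of grade 3 or higher, so the DLT count depends on it. So do the SAE, related-event, grade 3/4 and fatal-event rows of the overview table in SAP 8.10.1.2. Outcomes are exposed too, because Protocol 8.2.2.5 requires related AEs and SAEs to be followed until resolved, stable or back to baseline. An event that has not yet happened does not show up as a missing value, so a completeness check would not find it.

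**Working it through.** **Inputs.** Schedule: weekly for 6 weeks, then every 3 weeks, up to 20 injections (Protocol 3.1, Appendix II B). Post-dose window: 30 days (SAP 8.10.1). Safety visit: 30 to 44 days after the last dose (Protocol 6.2.6). End-of-treatment visit: within 7 days (Protocol 6.2.4). Patients treated: 6 (SAP 4). Interval method: exact Clopper-Pearson (SAP 8.1).

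**Reproducing the plan's own figures.** Injections 1 to 6 fall on Days 1, 8, 15, 22, 29 and 36. Injection 7 is on Day 43, and the rest follow every 21 days. This gives 9 injections by Day 85, matching the worked example in SAP 7.6.2. The 20th falls on Day 43 + 13 × 21 = Day 316. Counting the last 3-week interval, 6 + 14 × 3 = 48 weeks, and 336/30.4375 = 11.04 months. This agrees with the duration of around 11 months in Protocol 4.4.

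**Gap for a patient given all 20 injections.**

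| Event | Day | Days after last dose |
|---|---|---|
| SAP 7.5 condition met at the earliest | 316 | 0 |
| Latest end-of-treatment visit | 316 + 7 = 323 | 7 |
| Treatment-emergent window closes | 316 + 30 = 346 | 30 |
| Safety follow-up visit | 346 to 360 | 30 to 44 |

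On the more generous reading, in which treatment is complete only after the last 21-day interval, 30 − 21 = 9 days of the window remain. The visit is then still 9 to 23 days away.

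**Effect of one missed patient among 6.** The change is 1/6 = 16.7 percentage points.
- 0/6: the upper limit is 1 − 0.025^(1/6) = 45.9%, so the 95% CI is 0 to 45.9%.
- 1/6: the lower limit is 1 − 0.975^(1/6) = 0.4%, and the upper limit (97.5% quantile of Beta(2, 5)) is 64.1%.

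**Chance of missing at least one patient.** The documents give no late-event rate, so this is an assumption. Let p be the chance that a patient has a newly countable event in a wholly unobserved window, and k the number of patients so truncated. The chance is 1 − (1 − p)^k. For p from 5% to 30%, it is 5% to 30% with k = 1 and 10% to 51% with k = 2.

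**The case against.** The strongest reply is that SAP 7.5 states a readiness condition and does not order export on the day of the last dose. Draft outputs are reviewed before export (SAP 7.5) and before lock (SAP 8.1), and a data review meeting precedes lock (SAP 7.2). Protocol 8.2.2.2 bars eCRF entry after lock only for related SAEs arising more than 30 days after the last dose, which suggests that lock was expected after that point. The 30-day limit is also a rule for classifying events, not a follow-up requirement, so SAP 7.5 is silent about the window more than it contradicts it. All of this lowers the practical risk. None of it requires the window to have elapsed or fixes the export date.

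It is also unclear whether withdrawal in SAP 7.5 means from treatment or from the study. Protocol 4.3.2 asks that, as far as possible, nobody leave the study without the safety visit. On the second reading the gap lies mainly with patients who complete treatment, and they meet the condition at injection 20 on either reading.

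Four stronger readings may tempt a reader, and the documents do not support them.

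- **Scheduled laboratory data in the 30-day window would be lost.** SAP 8.10.2 does run its summaries to 30 days after discontinuation. But the last scheduled tests are at the end-of-treatment visit, and Protocol 6.2.6 and Appendix II B list none at the safety visit. Waiting for that visit adds no scheduled value.
- **The rule wrongly cuts off 9-weekly progression follow-up.** That follow-up runs until progression (Protocol 6.2.5), so a cut-off at the safety visit would not restore it. SAP 7.6.2 and 8.8 already censor at the last evaluable tumor assessment.
- **The share of unobserved time measures the bias.** The 30 days are 30/346 = 8.7% of the period after 20 injections, 30/66 = 45.5% after 6 and 30/31 = 96.8% after one. These are calendar shares that assume export on the day of the last dose. They are not estimates of missed events.
- **Data were in fact cut early.** SAP 4 reports that the study was stopped in October 2024, and SAP 1 cites a CRF dated 20 November 2024. The window may have closed before any export.

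**Conclusion.** The point stands as a gap in a stated rule. Taken literally, SAP 7.5 can be satisfied up to 30 days before the treatment-emergent window closes and up to 44 days before the safety visit, and no other provision in the available text delays export. Only patients last dosed within 30 days before export (for the window) or 44 days (for the visit) are affected. For such a patient, late AEs, DLTs, SAEs and AE outcomes could be missed. With 6 treated patients, each missed patient shifts a safety rate by 16.7 percentage points.

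Actual impact is unknown and may be nil, because the documents give no last-dose, lock or export date. The change is worth making because the primary endpoint is involved and the repair is small.

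**What to change.** Replace the timing sentence in SAP 7.5 with, for example: *The final analysis will be performed, and the database exported, only after every treated patient has had the safety follow-up visit (at least 30 days after the last dose), has died, or has been lost to follow-up.* Amend the cut-off definition in SAP 7.6.1 to match.

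This brings both sections into line with the SAP's own end-of-study definition. Name the safety visit explicitly: under a bare reference to the last visit, a reader could think the analysis must also wait for open-ended progression follow-up.

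The earliest analysis moves from Day 316 to Days 346 to 360 for a patient given 20 injections, a delay of at most about 44 days. Sample size, methods and visits do not change. If the last safety visit has already taken place, the change costs only the wording. In either case, the study report should give the last-dose date and the export date, so that a reader can confirm the window was complete for all 6 patients.

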## 7.6 Definitions and Derived variables

### 7.6.1 Definitions

Screened patient: A patient having consented

Re-screened patient: A patient who did not meet eligibility criteria when initially consented. This patient may fulfill criteria later and will be re-consented for screening.

Screened failed patient: A screened patient never treated in the study for any reason.

Treated patient: A patient having received at least one TG4050 dose.

Completed patient: Patient will be considered as completer if she received the treatment until:

- Disease progression or until the maximum number of administrations has been reached (20 injections of TG4050)
- occurrence of an AE due to DLT or linked to progressive disease
- Death

Baseline: Unless otherwise specified, baseline is the last measurement taken prior to the first injection of TG4050.

Baseline assessment for efficacy evaluations: In the context of baseline definition, the efficacy evaluations include in particular tumor evaluations and CA125 measurement. If baseline assessment is missing, results obtained at Day 1 can be used if assessments were performed prior to first TG4050 injection.

Baseline assessment for safety evaluations: the last available assessment before first TG4050 injection. If patients have no assessment as defined above, the baseline result will be missing. Baseline can be D1 if assessment was done before first TG4050 injection.

Study day:

- From first treatment administration, study day will be calculated using the start date of treatment as the origin, i.e. the study day will be calculated as (date of assessment) – (start date of study treatment) +1. Then study day 1 will be the first day of first study treatment administration.
- For pre-study treatment administration measurements, the study day will be negative and calculated as (date of assessment) – (start date of study treatment).

Cut-off date: For a given analysis (safety, final and follow-up analysis), data in the database with a date prior or equal to the cut-off date must be as clean as possible for the analyses. The cut-off date will be the date of the export.

Time window (to check visits out of this window):

- For the visits:
  - +/- 1 day for the first 6 weeks
  - +/- 7 days beyond the first 6 weeks
- For the tumor assessment:
  - Every 9 weeks with a time widow of +/- 7 days from start of treatment, CT-scan or MRI of the abdomen and pelvis are mandatory. Brain and chest CT are to be performed if lesions are suspected.

Progressive disease: as documented on tumor assessment according to RECIST 1.1.

Progressive disease will be determined according to RECIST (version 1.1) based on local evaluations. Lesions (non-target) identified at baseline, if any, will be followed post-baseline. The appearance of new lesions will also be investigated if clinically indicated.

**Tumor response:**

Tumor response status assessments will be evaluated by imaging performed every 9 weeks from first TG4050 administration until documented progression. Only tumor assessments performed before the start of further antineoplastic therapies (i.e. any additional secondary antineoplastic therapy or surgery) will be considered.

Per RECIST 1.1, the method used at baseline should match at all subsequent assessments, but, for a number of reasons such as site error (e.g. switch from MRI to CT) or renal dysfunction (making contrast a risk), this will not always be done. A strict implementation of RECIST would mean that any change in imaging method compared to one used at baseline should lead to unknown overall response at given assessment.

The number and percentage of patients with complete response among patients with non-measurable lesion at baseline will be presented.

**End of study:** The end of study is defined as the date of the last patient last visit (including safety follow-up visit). The end of study form in the eCRF will be filled in when patient withdraws the study due to any reason.

### 7.6.2 Derived variable

The following conventions will be used:

- 1 month corresponds to  $365.25/12=30.4375$  days.
- 1 year corresponds to 365.25 days.
- Temperature (°C):
  - from F to °C:  $\text{Temperature (°C)} = (\text{Temperature (F)} - 32) / 1.8$
- Weight (kg):
  - from Lbs to kg:  $\text{weight (kg)} = \text{weight (lbs)} \times 0.45$
- Height (cm):
  - from Inch to cm:  $\text{height (cm)} = \text{height(inch)} \times 2.54$

The following variables will be calculated:

- **Age in years:** the age at informed consent form (ICF) signature presented in whole years  
(year of ICF signature – year of birth)
- **Body Mass Index (BMI) expressed in kg/m^2:**  $\text{Weight (kg)} / \text{Height}^2 (\text{m}^2)$
- **Duration of an event (in days):** End date – Start date + 1
- **Time since initial diagnosis (Months):** (date of ICF signature – date of initial diagnosis)/30.4375

**Time to measurable relapse per RECIST 1.1 (months)** is defined as the time from the date of the first injection until relapse or documented progressive disease whichever occurs first. Time to measurable relapse will be censored if no progression is observed at the cut-off date for analysis. The censoring date will be the date of the last evaluable tumor assessment before the cut-off date.

Time to measurable relapse expressed in months =

((Date of documented relapse/disease progression) - date of first treatment injection) +1)/30.4375

or

(Date of last evaluable tumor assessment – date of first treatment injection +1)/30.4375 in case of censoring.

**Relative Dose intensity (RDI) (%)**: expressed as percentage and defined as the ratio of “delivered” to the “planned” dose intensity. As the dose is always the same ( $10^8$  / pfu), RDI is calculated as the ratio of number of injections received divided by the number of injections planned. A Relative Dose Intensity of 100% indicates that TG4050 was administered as planned, without delay and without cancellations.

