### 4.4. Definition of end of study

The end of study is defined as the date of the last patient last visit.

The end of study page in the eCRF will be filled in when patient withdraws the study due to any reason or if the patient dies or progresses. The patient will be considered as completer if she received the 20 injections or progresses or dies or withdraws due to a DLT before the end of treatment.

In addition, the shelf life of TG4050 is 48 months. Considering the planned duration of treatment lasting around 11 months with pre-treatment assessments of around 1 month (confirmation of asymptomatic relapse and baseline visit), patients will need to start treatment at least 12 months before the expiry date. Otherwise, patients will be withdrawn from the trial prior treatment period initiation and their end of study would be defined as the date of study withdrawal.

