### 2.1 Study parts

#### 2.1.1 Screening period

A screening period will start at least 6 months after completion of standard first-line treatment including a platinum-based chemotherapy. Only patients with histological confirmation of serous carcinoma of the ovary, fallopian tube or peritoneum and having high risk cancer defined as high grade and stage IIIC or stage IVA disease, who achieved a complete response after chemotherapy maintained for at least 6 months and from whom tumor tissue is available for tumor neoantigens identification can be included in the screening period.

For those patients, tumor tissue which have been banked at the time of surgery and blood samples will be tested for TSAs identification. TSAs will be used to manufacture an individualized TG4050 mutanome-directed immunotherapy. Manufacturing will take approximately 12 weeks for the vaccine to be prepared in accordance with GMP procedures.

During the screening period, patients will be regularly followed per standard medical practice: serum CA-125 measurements performed in an accredited central laboratory at least every 3 to 4 months and imaging in the event of CA-125 increase and/or clinical symptoms. If a suspicious but indeterminate nodule is identified at study entry, repeat imaging should be obtained 3 months after (+/- 2 weeks) to determine whether the nodule is malignant. Alternatively, a biopsy may be obtained. Patients who have developed an asymptomatic relapse according to the below definitions are eligible for the treatment period. If the patient did not relapse after 2 years of follow-up, this follow-up is performed at least every 6 months (+1 month) according to the investigator's standard practice.

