### Graphical study design:

## 2.2 Number of patients

The study will be conducted in France and US and involve 5 centers:

- An approximate number of 60 patients will be included in the screening period

Note: If some patients have not relapsed within 36 months after vaccine manufacture, they will be withdrawn from the study and will not be replaced.

- Cohort A: A least of 13 patients will be enrolled in the treatment period to allow sufficient number of patients evaluable for safety, efficacy and immunological analyses.
- Cohort B: a maximum of 10 patients to be included at the time of full accrual in cohort A.

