**Creatinine Clearance (CRCL):**

**Creatinine clearance equation could be expressed as 3 methods: Cockcroft / CKD EPI / MDRD**

With Cockcroft formula Creatinine Clearance will be recalculated:

$$\text{CRCL(Females)} \text{ (mL/min)} = 1.04 \times \text{weight (kg)} \times (140 - \text{Age}) / \text{creatinine}(\mu\text{mol/L})$$

$$\text{CRCL (Females)} \text{ (mL/min)} = [(140 - \text{age})(\text{weight (kg)}) \times (0.85)] / (72) \text{ (serum creatinine in mg/dL)}$$

For the remaining time points, creatinine and weight values of corresponding time points will be used. If weight is missing, the closest compared to the actual date weight will be used.

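### The SAP's age formula is one year too high for patients who consent before their birthday, and its pound factor of 0.45 makes weight and BMI 0.79% low; the effect on recalculated clearance is small and has no fixed sign

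*SAP*

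**What the plan says.** SAP 7.6.2 describes age as "the age at informed consent form (ICF) signature presented in whole years" and gives the formula as "year of ICF signature – year of birth". The same list converts pounds to kilograms with a factor of 0.45 and defines BMI as weight in kilograms over height in metres squared.

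The creatinine clearance entry that follows states: "With Cockcroft formula Creatinine Clearance will be recalculated". The formula uses weight, age and creatinine. For later visits it adds: "For the remaining time points, creatinine and weight values of corresponding time points will be used". Age is not mentioned there, and age at consent is the only age that the SAP defines.

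Age is reported for the screened and treated populations (SAP 8.3.1 and the section 10.1 table list) and in the adverse event listing (SAP 8.10.1.2).

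**The concern.** Whole years at a given date ordinarily means completed years. A difference of calendar years is something else: it ignores whether the birthday has passed. The data to do it properly exist. Protocol 6.1.1 collects date of birth, Protocol 14.1 requires it in source documents, and SAP 7.3 already uses it to impute medication start dates.

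The pound factor stands out against the SAP's own standard. Inches use 2.54, temperature uses 1.8, months use 30.4375 days, and Appendix 2 carries its conversion factors to four or more significant digits.

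At stake is the accuracy of reported age, weight and BMI and, through the Cockcroft formula, of recalculated clearance.

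**Working it through.** **Inputs.** The age formula, the factor 0.45 and the Cockcroft formula are from SAP 7.6.2. One pound is 0.45359237 kg by definition. Six patients were treated (SAP 4). Assumptions: birth and consent dates are independent and spread evenly over the year; some weights were recorded in pounds; age at consent is the age used in the clearance formula.

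**Age.** Calendar-year difference minus completed years at consent is 0 if the birthday has passed and +1 if it has not. It is never negative. Under even spread the share with +1 is 0.50, so mean age is overstated by about 0.5 year. The chance that at least one of the six treated patients is affected is 1 − 0.5^6 = 98%.

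**Weight and BMI.** 0.45 / 0.45359237 = 0.99208, which is 0.79% low. At 150 lb, weight is 67.50 kg instead of 68.04 kg. With an assumed height of 1.63 m, BMI is 25.41 instead of 25.61. Age does not enter BMI, and patients weighed in kilograms are unaffected.

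**Clearance with age held at consent.** The ratio of SAP value to correct value is [(140 − age − 1) / (140 − age)] × 0.99208 when both errors apply:

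- Age 45: 94/95 × 0.99208 = 0.9816, or 1.8% low; a true 45 mL/min becomes 44.17.
- Age 60: 79/80 × 0.99208 = 0.9797, or 2.0% low; 45 becomes 44.09.
- Age 75: 64/65 × 0.99208 = 0.9768, or 2.3% low; 45 becomes 43.96.

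**Clearance with age frozen at consent and the test done later.** The gap can be long. "Manufacturing will take approximately 12 weeks" before treatment is possible. At the other end, "If some patients have not relapsed within 36 months after vaccine manufacture, they will be withdrawn from the study". Treatment itself has a "planned duration of treatment lasting around 11 months" (Protocol 4.4). The gap from consent to a test therefore runs from about 12/52 = 0.23 year to about 0.23 + 3 + 11/12 = 4.15 years.

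The table gives the mean error against clearance computed with completed age on the test day, for an SAP age of 60, from a simulation under the even-spread assumption.

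| Gap from consent | Weighed in kg | Weighed in lb |
|---|---|---|
| 0 | −0.6% | −1.4% |
| 0.25 y | −0.3% | −1.1% |
| 0.5 y | 0.0% | −0.8% |
| 1 y | +0.6% | −0.2% |
| 2 y | +1.9% | +1.1% |
| 3.25 y | +3.6% | +2.7% |
| 4.15 y | +4.8% | +4.0% |

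The whole-year rows can be checked by hand. At 2 years the completed age is 61 or 62 with equal chance, so the mean ratio is (80/79 + 80/78)/2 = 1.019, and × 0.99208 = 1.011.

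The sign changes at about 0.5 year for kilograms. For pounds, an age understated by 80 × (1 − 0.99208) = 0.63 year cancels the weight effect. The mean age error is 0.5 minus the gap, so that happens at about 1.13 years.

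**The case against.** A reader might infer that age too high and weight too low always push clearance down, and that US patients near 45 mL/min could then be coded as major eligibility deviations (INC11 in SAP Appendix 1). The documents support neither step.

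- **Direction.** Read literally, the SAP keeps age at consent while creatinine and weight move forward. Even at the baseline test, done after manufacture and at relapse, the mean error can fall on either side of zero.
- **Eligibility.** Protocol 6.2.1 has the investigator establish eligibility, and SAP 8.5.1 reports eligibility deviations as collected in the eCRF. Patients may also qualify by methods other than Cockcroft, whereas the SAP gives a recalculation only for Cockcroft. No route from the recalculated value to INC11 is described.

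Two further objections concern weight of consequence. Clearance is not among the CTCAE-graded parameters in SAP Appendix 3, and no output title names it. Also, the calendar-year difference has mean error zero against exact decimal age, so it could be defended as a rough rounding.

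The first limits the size of the point, and I accept it. The second does not rescue the formula. The SAP reports individual ages in whole years, and for a given patient the result can be a year above her completed age although her date of birth is on file.

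**Conclusion.** Both derivations are wrong as written. Age is overstated by one year for patients consented before their birthday: about half, on the even-spread assumption. Weight and BMI are 0.79% low for patients weighed in pounds, if there are any.

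Clearance is at most about 2.3% low over ages 45 to 75 if age is held at consent. It has no fixed direction once elapsed time is counted. That age at consent enters the formula is an inference from the absence of any other defined age, and that silence is itself a small gap in the SAP.

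The point is minor. It affects descriptive output on six treated patients and on the screened population. No eligibility consequence is documented, and no efficacy or safety conclusion turns on it.

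**What to change.** In SAP 7.6.2:

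1. Derive age in completed years from date of birth and date of ICF signature.
2. Replace 0.45 with 0.45359237 kg per pound.
3. State that clearance uses age at the date of the assessment, as already specified for weight and creatinine.

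The first two are one line of code each and the third is a small change to the clearance derivation. No new data are needed. Age, weight, BMI and clearance displays have to be rerun if drafts exist. One consequence to know: completed years lie on average half a year below exact age, so clearance will sit slightly above a decimal-age calculation (0.5/80, about 0.6% at age 60). That follows from reporting age in whole years and is no reason to keep the present formula.
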